11.2 Serious Adverse Experiences (SAE)

An SAE is defined as any AE occurring at any dose that results in any of the following outcomes:

2. death
3. a life-threatening adverse experience
4. inpatient hospitalization or prolongation of existing hospitalization
5. a persistent or significant disability/incapacity
6. a congenital anomaly/birth defect

Other important medical events may also be considered an SAE when, based on appropriate medical judgment, they jeopardize the subject or require intervention to prevent one of the outcomes listed.

11.2.1 Serious Adverse Experience Reporting

Study sites will document all SAEs that occur (whether or not related to study drug) per [UCSF IRB Guidelines](#). The collection period for all SAEs will begin after informed consent is obtained, after study drug is administered for at least one dose, and will end after procedures for the final study visit have been completed.

All serious and non-serious adverse events will be collected in an adverse event reporting form. This information will be supplied to the Data Safety Monitoring Board (DSMB) and all adverse event information will be summarized and published in the final study publication.

In accordance with the standard operating procedures and policies of the local Institutional Review Board (IRB)/Independent Ethics Committee (IEC), the site investigator will report SAEs to the IRB/IEC and DSMB per UCSF IRB guidelines.

During the study, safety will be monitored by a 3-member Data Safety Monitoring Board (DSMB) which will be led by a pediatric headache specialist. The DSMB will review all study procedures before the initiation of the study. They will have the full and final authority to stop the study for any safety concern at any point. They will also review study data at the midpoint of the study, and at any subsequent interval that they recommend. Interim reports to the DSMB will be blinded to treatment status, though the DSMB may request unblinded information from the investigators at any time for any reason. Reports to the DSMB will be prepared by a UCSF Dept of Epidemiology and Biostatistics faculty member who is not otherwise involved in the study and who will not communicate with the study investigators regarding any aspect of the DSMB reports.

Serious and unexpected adverse events associated with the use of the study drug or procedures will be reported to the IRB and DSMB with subsequent follow-up submission of a detailed written report in accordance with the respective policies and procedures of the IRB. <http://irb.ucsf.edu/adverse-event>

Written IND Safety Reports will be submitted to the FDA as soon as possible and, in no event, later than 15 calendar days following the investigator-sponsor's receipt of the respective adverse event information.

The FDA will be notified by telephone or facsimile transmission of a human adverse event that is fatal or life-threatening no later than 7 calendar days after receiving the respective human adverse event information, followed by the subsequent submission of a written IND Safety Report

12 DISCONTINUATION AND REPLACEMENT OF SUBJECTS

12.1 Early Discontinuation of Study Drug

A subject may be discontinued from study treatment at any time if the subject, the investigator feels that it is not in the subject's best interest to continue. The following is a list of possible reasons for study treatment discontinuation:

- Subject withdrawal of consent (or assent)
- Subject is not compliant with study procedures
- Adverse event that in the opinion of the investigator would be in the best interest of the subject to discontinue study treatment
- Protocol violation requiring discontinuation of study treatment
- Lost to follow-up
- Positive pregnancy test (females)
- If a subject is withdrawn from treatment due to an adverse event, the subject will be followed and treated by the Investigator until the abnormal parameter or symptom has resolved or stabilized.

All subjects who discontinue study treatment should be encouraged to complete all remaining scheduled visits and procedures.

All subjects are free to withdraw from participation at any time, for any reason, specified or unspecified, and without prejudice.

Reasonable attempts will be made by the investigator to provide a reason for subject withdrawals. The reason for the subject's withdrawal from the study will be specified in the subject's source documents.

If the study (in part or in entirety) is discontinued for any reason, the UCSF sponsor-investigator will notify all other investigators, sub-investigators and study staff within FDA guidelines. Since melatonin at 3mg and at 6mg can be stopped without weaning, there will be no further data collected to ensure subject safety. If part of the study is discontinued, subjects will be reconsented with an updated consent as soon as it is approved by the IRB. All parts of the study that have been discontinued will be ended within FDA guidelines.

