these two tasks, and to provide a link to their headache diary. If they do not complete the headache diary, a reminder text will be sent the next morning. If they do not complete the headache diary for three days in a row, a study staff member will call to check in and remind them to do it and answer any questions. There will be a scheduled check in call at the four-week mark and again at the 8-week mark. If they provide headache diary data on $\geq 80\%$ of days in each 28-day period, they will receive a \$5 gift card each month. Once they have completed the 8-weeks of placebo treatment, they will return their study medication in a self-addressed envelope via FedEx.

10.3 Assessment of randomization eligibility (Day 57):

If the participant meets randomization criteria, the study pharmacy (Safeway) will be notified by study staff and the study pharmacy will review the randomization scheme to assign treatment and will enter this data into the study database. The study medication will be shipped to the participant's shipping address via FedEx.

Study staff will track the shipment via FedEx's tracking number on their website. Once the package shows as delivered, study staff will enter this information into the study database and a text message will be sent to the parent's smartphone asking them to confirm receipt of the study medication. The date the parent confirms receipt of the study medication will be day 1 of the randomized treatment phase.

10.4 8-week randomized treatment phase (Weeks 9-16):

Participants will take the study medication nightly and complete a headache diary nightly. A text message will be sent from the study database each evening at 9:00 PM to remind them to do these two tasks, and to provide a link to their headache diary. If they do not complete the headache diary, a reminder text will be sent the next morning. If they do not complete the headache diary for three days in a row, a study staff member will call to check in and remind them to do it and answer any questions. There will be a scheduled check in call at the four-week mark and again at the 8-week mark. If they provide headache diary data on $\geq 80\%$ of days in each 28-day period, they will receive a \$5 gift card each month. Once they have completed the 8-weeks of treatment, they will return their study medication in a self-addressed envelope via FedEx.

10.5 Study completion (Day 113):

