At the end of the 8-week randomized treatment phase there will be a study completion phone visit. We will again assess the PedMIDAS and CASQ scores. We will query for adverse events, and will solicit participant and parent feedback on the study design. We will remind participants to mail back the study medication bottle using the self-addressed FedEx envelope, and once this is received we will perform both a manual pill count and compare to the self-report count in their diary.

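### Section 12.1 rules out further safety data after a study stop because melatonin needs no weaning; that reason covers withdrawal monitoring only, and read literally the sentence waives a closing adverse-event query at a full stop

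*Combined protocol and SAP*

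**What the plan says.** The last paragraph of Section 12.1 applies when the whole study or a part of it is discontinued, whatever the reason. After a line on notifying investigators and staff, it says: "Since melatonin at 3mg and at 6mg can be stopped without weaning, there will be no further data collected to ensure subject safety". For a partial stop it adds: "If part of the study is discontinued, subjects will be reconsented with an updated consent as soon as it is approved by the IRB". It closes with a general statement that discontinued parts will be ended within FDA guidelines.

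Earlier in the same section are two rules for individual participants. For a subject withdrawn from treatment because of an adverse event, "the subject will be followed and treated by the Investigator until the abnormal parameter or symptom has resolved or stabilized". More generally, "All subjects who discontinue study treatment should be encouraged to complete all remaining scheduled visits and procedures".

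Elsewhere:
- Section 11.2.1 gives the DSMB power to stop the trial: "They will have the full and final authority to stop the study for any safety concern at any point".
- Section 11.2.1 has SAE collection begin after consent and a first dose, "and will end after procedures for the final study visit have been completed".
- Section 10.5 places the completion phone visit at the end of the 8-week randomized phase (Day 113), and says of it: "We will query for adverse events, and will solicit participant and parent feedback on the study design".
- Sections 10.2 and 10.4 provide for calls in each phase: "There will be a scheduled check in call at the four-week mark and again at the 8-week mark". Appendix 1 marks adverse-event review at each of these calls, but not at Visit 1.

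**The concern.** The reason and the rule do not match. That melatonin can be stopped abruptly is an argument about what happens after the last dose. It says nothing about events that began on treatment and have not yet been reported, or are still unresolved, when the study is stopped. Yet the rule drawn from it is worded for all further safety data, and its trigger has no exception for a stop made because of safety.

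At stake is completeness of the safety record in a trial of 10- to 17-year-olds. Adverse events are actively asked about only at the scheduled calls, so some days of exposure are always waiting for the next query. After a safety stop, those days fall just before the decision, when a complete count is most useful. Section 11.2.1 also undertakes to summarize and publish all adverse-event information. Site staff would have to settle the meaning of the sentence during the stop itself.

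**Working it through.** **Step 1: the text, for a full stop**

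| Provision | Where | Does it clearly supply a safety close-out at a full stop? |
|---|---|---|
| Closing adverse-event query | 10.5 | No. It is tied to the end of the randomized phase. |
| Early-termination or study-stop visit | Appendix 1 | None is listed. |
| Encourage remaining visits | 12.1 | Arguable. The wording covers all who stop treatment, but it presumes that visits are still running. Study termination is not among the listed reasons. |
| Follow adverse events to resolution or stabilization | 12.1 | Only for subjects withdrawn because of an adverse event. Not expressly cancelled, but in conflict with the no-further-data sentence. |
| End of SAE collection | 11.2.1 | Defined, but by a final visit that a full stop may cancel. Section 12.1 read literally would end collection at the stop. |
| Ending within FDA guidelines | 12.1 | Names no query and no collection window. |
| Phone reports by families; IRB and FDA reporting | Synopsis; 11.2.1 | Still apply. The first is passive; the second acts on information received. |

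A partial stop is much less affected: calls continue and participants are reconsented.

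**Step 2: how many participants**

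The plan gives no figure to reproduce. Inputs: 210 enrolled over 24-30 months (4.1); two 8-week phases (4.1); 25% lost at the run-in and 85% completion (14.6); 1:1:1 allocation (8.1). Assumptions: uniform accrual, run-in failures leave at Day 57, and a month is 30.44 days.

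- Accrual: 210/30 = 7.0 to 210/24 = 8.75 per month.
- Phase length: 56/30.44 = 1.84 months.
- In run-in on placebo: 7.0 x 1.84 to 8.75 x 1.84 = 12.9 to 16.1.
- In randomized treatment: x 0.75 = 9.7 to 12.1.
- Total on study: 22.5 to 28.2.
- On melatonin: 2/3 of those randomized = 6.4 to 8.0. If the 15% dropout is spread evenly through the phase, x 0.925 = 6.0 to 7.4.

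These hold from 112/30.44 = 3.7 months after first enrolment to the end of accrual. If 24-30 months is the total study duration, as the Synopsis also puts it, accrual takes 20.3-26.3 months, giving 26-33 on study and 7.3-9.5 on melatonin.

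**Step 3: how much exposure and how many events**

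With queries every 28 days the mean time since the last one is 14 days, so 6.4 x 14 to 8.0 x 14 is about 90-113 melatonin participant-days. Four weeks is only approximate as an upper limit: run-in weeks 1-4 have no earlier query, shipping delays the start of the randomized phase, and Appendix 1 allows a window of 3 business days either way.

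For illustration, Section 1.2 cites 12% tiredness over three months (taken as 91 days) in an open-label study of 60 children:

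| Onset assumption | Per participant | New events not yet queried |
|---|---|---|
| Constant hazard | 1 - 0.88^(14/91) = 1.95% | 0.125 to 0.157 |
| Uniform over the first 28 days | 0.5 x 0.12 x 0.5 = 3% | 0.19 to 0.24 |
| All on day 1 | 0.5 x 0.12 = 6% | 0.39 to 0.48 |

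The leading 0.5 in the last two rows is the half of treated participants who are in their first 28 days. Events already open at the stop are additional; the documents do not quantify them, and they give no serious-event rate to apply.

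**The case against.** The best defence is that the sentence carries its own limit: it opens with weaning, so it means only that no withdrawal monitoring is needed, and the promise to end within FDA guidelines does not fit a plan to abandon safety duties. That may well be the intent. But the operative words are not limited in that way, and if that is the intent, saying so costs the sponsor nothing.

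Second, the rule on remaining visits covers everyone who discontinues treatment, and a full stop makes every treated participant do so. On its wording it could reach the remaining calls and the completion query. This stands as a possible reading, but it leaves two rules in one section that contradict each other.

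Third, the consequence is slight: a fraction of one expected event, for mild tiredness, from an open-label study of ages 5-15 dosed by weight. This stands. The DSMB may also request unblinded information at any time, although it can see only what has been collected.

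Two stronger readings are tempting. A reader might infer that the protocol has no defined end of SAE collection; Section 11.2.1 defines one, and the fault is that it hangs on a visit a full stop may cancel. A reader might also infer that all safety follow-up is cancelled; the adverse-event follow-up rule is not expressly withdrawn, and phone, IRB and FDA reporting remain.

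**Conclusion.** The point holds as a defect of wording with a small safety consequence. The stated reason justifies omitting withdrawal monitoring, whereas the sentence omits more than that. Taken literally, it removes the closing adverse-event query at a full stop and contradicts its own section, and it leaves the end of SAE collection unreconciled with Section 11.2.1.

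The size rests on uniform accrual and the plan's own run-in and allocation figures; the event counts also rest on a borrowed tiredness rate and are an illustration only. The point depends on an early stop, which is not planned (Section 14.5 foresees no interim analysis), and the primary analysis is unaffected if the trial runs to completion. Severity: minor.

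**What to change.** Replace the sentence in Section 12.1 with:

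> No tapering or withdrawal monitoring is needed. If the study or a part of it is stopped, each participant in the stopped part has the completion phone call with an adverse-event query; this call is the final study visit for SAE collection under 11.2.1; adverse events open at that call are followed until resolved or stabilized.

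This keeps the sponsor's point about weaning and settles all three inconsistencies. The cost is one change of protocol wording now. Only if a full stop occurs does it add about 25 phone calls (26-33 under the shorter accrual period), of a kind already planned, and follow-up of the few events still open.

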12.2 Withdrawal of Subjects from the Study

A subject may be withdrawn from the study at any time if the subject or the investigator, thinks it is not in the subject's best interest to continue.

All subjects are free to withdraw from participation at any time, for any reason, specified or unspecified, and without prejudice.

Reasonable attempts will be made by the investigator to provide a reason for subject withdrawals. The reason for the subject's withdrawal from the study will be specified in the subject's source documents.

12.3 Replacement of Subjects

Subjects who withdraw from the study treatment will not be replaced.

Subjects who withdraw from the study will not be replaced.

13 PROTOCOL VIOLATIONS

A protocol violation occurs when the subject or investigator fails to adhere to significant protocol requirements affecting the inclusion, exclusion, subject safety and primary endpoint criteria. Protocol violations for this study include, but are not limited to, the following:

Failure to meet inclusion/exclusion criteria

Use of a prohibited concomitant medication

Failure to comply with Good Clinical Practice (GCP) guidelines will also result in a protocol violation. The Investigator will determine if a protocol violation will result in withdrawal of a subject.

When a protocol violation occurs, it will be discussed with the investigator and a Protocol Violation Form detailing the violation will be generated. This form will be signed by the

Investigator. A copy of the form will be filed in the site's regulatory binder and in the Investigator's files.

14 STATISTICAL METHODS AND CONSIDERATIONS

14.1 Data Sets Analyzed

All eligible patients who are randomized and receive at least one dose of the study drug (the Safety Population) will be included in the safety analysis.

[name] will analyze the data using STATA. As a UCSF KL2 Scholar, she will have assistance from the UCSF Dept. of Epidemiology and Biostatistics faculty and CTSI consulting services as needed for statistical issues.

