8.4.2 Dispensing

A medication bottle will be given to participants at the enrollment visit for the single blind placebo phase. For those eligible to continue to the 8-week double blind phase, the pharmacy will ship the final study drug bottle to the participant's home.

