8.4.3 Administration Instructions

Participants will take the study drug (either 3 mg melatonin, 6 mg melatonin or placebo) orally at night one hour before bedtime (approximately 21:00 hours).

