9.1.6 Adverse Events

Information regarding occurrence of adverse events will be captured throughout the study. Duration (start and stop dates and times), severity/grade, outcome, treatment and relation to study drug will be recorded on the case report form (CRF).

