10 EVALUATIONS BY VISIT

10.1 Visit 1 (Screening and Enrollment, Day 1)

We will do a one-time enrollment visit at either UCSF or UCLA.

Consent/assent: At the start of an enrollment visit, potential subjects and their parent/guardian will be told about the study by a study investigator and/or study coordinator and will be provided with an informed consent document to review. For 12-17 year-olds, the informed consent document is addressed to the adolescent and is to be signed by both the adolescent and their parent/guardian. For 10-11 year-olds, the parent will sign the consent form and the participant will be provided with a simplified assent document. For this group the participant's assent will be documented by a study team member. Participants and parents/guardians will be given the opportunity to ask questions and have them answered to their satisfaction before deciding whether to participate. Consent and HIPPA can be signed with paper/pen or via DocuSign.

Enrollment visit data:

The enrollment visit data will be entered directly into the study database during the enrollment visit. Demographic and logistical information will be collected including name, age, sex, race/ethnicity, shipping address, participant smartphone number, parent smartphone number, and best times for follow-up calls. A pediatric headache neurologist will review the headache history to ensure the participant meets ICHD criteria for migraine with or without aura and will review the current medication list and past medical history. We will measure weight, blood pressure, pulse, and respiratory rate. There will be a general medical examination and a neurologic examination. Girls who have had their first period will undergo a urine pregnancy test. Baseline assessment of the PedMIDAS score and CASQ score will be assessed. Participants will be taught how to use the headache diary on their smartphone. They will be given the study medication for the single-blind placebo treatment phase and instructed to take study medication 1 hour before bedtime.

10.2 8-week single-blind placebo treatment phase (Weeks 1-8):

Participants will take the study medication nightly and complete a headache diary nightly. A text message will be sent from the study database each evening to remind them to do

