14.4 Analysis of Secondary Endpoints

Secondary outcome measures will include $\geq 50\%$ responder rates, tolerability (as measured by CASQ scores), and need for use of acute headache medications. Safety and tolerability data will be summarized by treatment group. Adverse event rates will be coded by body system. Adverse events will be tabulated by treatment group and will include the number of patients for whom the event occurred, the rate of occurrence, and the severity and relationship to study drug.

Secondary outcomes:

(We will control for the baseline level of these outcomes in all of these analyses)

Effectiveness secondary outcomes:

1. Number of migraine/migrainous days in the 5th-8th weeks of randomized treatment between **melatonin 3 mg vs. placebo**.

2. Number of migraine/migrainous days in the 5th-8th weeks of randomized treatment between **melatonin 6 mg vs. placebo**.
3. Number of migraine/migrainous days in the 5th-8th weeks of randomized treatment between **melatonin 3 mg vs. 6 mg**.
4. Mean headache days in 5th-8th randomized phase in melatonin (combined) vs. placebo, (followed by melatonin 3 mg vs. placebo, melatonin 6 mg vs. placebo, and melatonin 3 mg vs. melatonin 6 mg using t-tests).
5. Mean acute medication use days in 5th-8th randomized phase in melatonin (combined) vs. placebo, (followed by melatonin 3 mg vs. placebo, melatonin 6 mg vs. placebo, and melatonin 3 mg vs. melatonin 6 mg using t-tests).
6. Mean PedMIDAS score (continuous) in 5th-8th randomized phase in melatonin (combined) vs. placebo, (followed by melatonin 3 mg vs. placebo, melatonin 6 mg vs. placebo, and melatonin 3 mg vs. melatonin 6 mg using t-tests).
7. $\geq 50\%$ responder rate in 5th-8th randomized phase in melatonin (combined) vs. placebo (Chi-square or Fisher's exact (if needed), (followed by melatonin 3 mg vs. placebo, melatonin 6 mg vs. placebo, and melatonin 3 mg vs. melatonin 6 mg using Chi-square (or Fisher's exact)).

Safety outcomes:

1. Proportion with adverse events between groups
 - a. Proportion with serious adverse events between groups
 - b. Proportion of adverse events thought to be related to the study treatment
2. Mean Sleepiness score in 5th-8th randomized phase in melatonin (combined) vs. placebo, (followed by melatonin 3 mg vs. placebo, melatonin 6 mg vs. placebo, and melatonin 3 mg vs. melatonin 6 mg using t-tests).

Trial design assessment outcome:

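### The safety set admits only eligible patients and does not tie its one-dose condition to randomised treatment, and the adverse event comparison it feeds has no onset window

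*Combined protocol and SAP*

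**What the plan says.** **Who is in the set.** Section 14.1 names one analysis set, for safety: "All eligible patients who are randomized and receive at least one dose of the study drug (the Safety Population"). Section 6.1 uses *eligible* for subjects who satisfy the inclusion and exclusion criteria. Section 13 lists "Failure to meet inclusion/exclusion criteria" among the protocol violations and adds: "The Investigator will determine if a protocol violation will result in withdrawal of a subject".

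**What counts as study drug.** The protocol does not define the term. Section 8.4.3 reads "Participants will take the study drug (either 3 mg melatonin, 6 mg melatonin or placebo) orally at night one hour before bedtime", which lists the three randomised options, and Section 8.4.1 is similar. Section 8.4.2 says that for the double-blind phase "the pharmacy will ship the final study drug bottle", which implies that the run-in bottle was study drug too. Appendix 1 marks study drug dispensing at Visit 1, when the run-in starts, and again at Visit 3. Section 10.1 says of enrolled participants: "They will be given the study medication for the single-blind placebo treatment phase".

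**Which events count.** Section 9.1.6 states: "Information regarding occurrence of adverse events will be captured throughout the study". Appendix 1 reviews adverse experiences at Visits 2 to 5, two of which fall in the run-in. Section 11.2.1 starts SAE collection after consent and a first dose, not at randomisation. Section 14.4 lists the outcome "Proportion with adverse events between groups" with no start date for the events. The sleepiness score in the same list is confined to weeks 5–8 of the randomised phase.

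**The concern.** A safety set is normally defined by exposure. Making eligibility a condition of entry removes people who took the treatment because of something found out about them, possibly after they were dosed. The exclusion criteria in Section 6.3 include a history of seizures, pregnancy and nocturnal asthma, so a participant enrolled in error may be one whose safety data matter particularly.

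The other two gaps concern the contrast between arms. If a run-in capsule satisfies the one-dose condition, a participant who was randomised but never opened the second bottle still sits in an arm's denominator. If events from the 8-week placebo run-in are counted by arm, every arm carries the same background, and a real difference between melatonin and placebo looks smaller than it is.

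**Working it through.** **1. Can a dosed participant fall outside the set?** Three sections together give the answer.
- Section 6.1: eligible means meeting the inclusion and exclusion criteria.
- Section 13: failing those criteria is a violation, and withdrawal is decided case by case.
- Section 14.1: only eligible patients enter the safety analysis.

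A participant can therefore be ineligible, randomised, dosed and kept in the study, yet be outside the set on its literal wording. Nothing in Section 14 restores that person to the arm comparison.

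**2. How many?** The plan gives no figure for the Safety Population. Section 14.6 gives the number expected to be randomised. Its enrolment target comes from 42 / 0.85 / 0.75 = 65.9 per arm, set at 70, or 210 in total. With 25% lost in the run-in, 210 × 0.75 = 157.5 are randomised. The ineligible fraction is an assumption:
- 2%: 157.5 × 0.02 = 3.2
- 5%: 157.5 × 0.05 = 7.9

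That is about 3 to 8 people.

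**3. Does the one-dose condition screen anyone out?** Under the broad use of the term (Section 8.4.2, Appendix 1), anyone who took a run-in capsule has met it before randomisation. Under the narrow use (Sections 8.4.1 and 8.4.3), a randomised-phase dose is needed. The two differ for participants assigned treatment who never take it. That can happen, because Section 10.3 has the pharmacy assign treatment before shipping. The numerical effect is small. If a fraction f of the melatonin group never took a randomised capsule, an event risk of 12% becomes 0.12 × (1 − f): 11.8% at f = 2% and 10.8% at f = 10%. The 12% is the tiredness figure that Section 1.2 quotes from the 60-child open-label study, and f is assumed.

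**4. What if run-in events are counted by arm?** Let r be the risk of a run-in event, equal in all arms, and p the randomised-phase risk, with the phases independent. Then

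risk of any event = 1 − (1 − r)(1 − p), so the difference between arms = (1 − r)(p_melatonin − p_placebo).

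With assumed p of 20% on placebo and 35% on melatonin:

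| r | Placebo | Melatonin | Difference (points) |
|---|---|---|---|
| 0 | 20% | 35% | 15 |
| 10% | 28% | 41.5% | 13.5 |
| 20% | 36% | 48% | 12 |
| 30% | 44% | 54.5% | 10.5 |
| 40% | 52% | 61% | 9 |

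A second assumed pair, 15% against 30%, shows the effect on the risk ratio and on power. Power is for 52 placebo and 104 melatonin participants, two-sided 5%, normal approximation:

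| r | Difference (points) | Risk ratio | Power |
|---|---|---|---|
| 0 | 15 | 2.00 | 53% |
| 5% | 14.25 | 1.74 | 45% |
| 15% | 12.75 | 1.46 | 34% |
| 30% | 10.5 | 1.26 | 23% |

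The absolute difference shrinks by the factor (1 − r) whatever p is. The size of r is unknown.

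**The case against.** **Events of ineligible participants are not lost.** A reader might infer that they vanish. They do not. Section 11.2.1 puts all serious and non-serious events on the reporting form, sends them to the DSMB and has them summarised in the publication, with no eligibility limit. This stands, and it confines the point to the arm-level comparison. It does not remove the point, because the same section keeps interim DSMB reports blinded to treatment unless the DSMB asks otherwise.

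***Eligible* may mean only that the participant passed the run-in.** Sections 8.4.2 and 10.3 use the word in that sense. The reading is possible, but Section 14.1 does not adopt it and Section 6.1 points the other way. Section 13 names a violation category; it does not predict that ineligible participants will be dosed.

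***Study drug* may mean randomised treatment only.** Sections 8.4.1 and 8.4.3, and the order of words in 14.1, favour this. The term is ambiguous rather than plainly tied to the run-in. Nor can one say that every randomised participant has already met the condition: the randomisation criteria in Section 6.3 require migraine days and diary entries, not a capsule taken.

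**No section says that run-in events are compared between arms.** This is correct. A population definition settles who is analysed, not which events count. The gap is the missing window in Section 14.4.

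**Sleepiness is protected.** Section 2.1 treats daytime sleepiness as essentially the only reported risk, and its score has a randomised-phase window. This stands for the score, but not for sleepiness reported as an adverse event.

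**Conclusion.** The point holds in three limited parts.

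1. On its literal wording, Section 14.1 removes randomised, dosed participants found to be ineligible from the arm-level safety comparison. Their events still reach the DSMB and the overall summary. The number is about 3 to 8 if 2–5% of about 158 are ineligible, which is an assumption.
2. *Study drug* is used for both run-in placebo and randomised treatment, so the one-dose condition may exclude almost nobody.
3. Section 14.4 leaves open whether run-in events count in the arm comparison. If they did, an assumed 15-point difference would appear as 13.5 to 9 points for assumed run-in risks of 10–40%. The direction is dilution towards no difference. It is not a bias favouring one arm's event count, since randomisation balances run-in events on average.

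A reader might go further and conclude that the plan hides harm or deliberately counts pre-randomisation events by arm. The documents support neither. The primary efficacy analysis is not affected.

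**What to change.** **Section 14.1.** Delete *eligible*. Define the Safety Population as all randomised participants who took at least one dose of double-blind randomised-phase treatment, regardless of eligibility.

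**Section 14.4.** Compare arms on adverse events with onset or worsening on or after the first randomised-phase dose. Tabulate run-in events separately.

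Use the first dose as the start, not Day 1 of the randomised phase. Section 10.3 sets Day 1 as the date the parent confirms receipt of the bottle, which need not be the date of the first capsule. The nightly diary records whether the capsule was taken (Sections 8.5 and 8.6), and event start dates and times are on the CRF (Section 9.1.6). State what date applies if the first diary entries are blank.

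The cost is a few lines of text before the blind is broken. The plan already collects the dates, so no new data and no change to sample size are needed.
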